#### 2.1.2 Subject recruitment

Subjects will be recruited by one or more of following means:

1. Posting study details on The University of Manchester's 'Research Volunteers' website.
2. Correspondence to existing wearers on the Eurolens Research database of subjects.
3. Advertising through a variety of media via a format separately approved by Manchester UREC.

#### 2.1.3 Inclusion criteria

Subjects will only be eligible for the study if:

1. They are of legal age (18) and capacity to volunteer.
2. They understand their rights as a research subject and are willing and able to sign a Statement of Informed Consent.
3. They are willing and able to follow the protocol.
4. They agree not to participate in other clinical research for the duration of this study.
5. They have a contact lens spherical prescription between -1.00 to -6.00D (inclusive)
6. They have a maximum of -1.00DC ocular astigmatism in each eye.
7. They can be satisfactorily fitted with the study lens types.
8. At dispensing, they can attain at least 0.20 logMAR distance high contrast visual acuity in each eye with the study lenses within the available power range.
9. They currently use soft contact lenses or have done so in the previous six months.
10. They are willing to comply with the wear schedule (at least five days per week and for at least eight hours per day).
11. They own a wearable pair of spectacles.

#### 2.1.4 Exclusion criteria

Subjects will not be eligible to take part in the study if:

1. They have an ocular disorder which would normally contra-indicate contact lens wear.
2. They have a systemic disorder which would normally contra-indicate contact lens wear.
3. They are using any topical medication such as eye drops or ointment.
4. They have had cataract surgery.
5. They have had corneal refractive surgery.
6. They have any corneal distortion resulting from previous hard or rigid lens wear or have keratoconus.
7. They are pregnant or breast-feeding.
8. They have any ocular abnormality which would, in the opinion of the investigator, normally contraindicate contact lens wear.
9. They have any infectious disease which would, in the opinion of the investigator, contraindicate contact lens wear or pose a risk to study personnel, or they have any immunosuppressive disease (e.g. HIV), or a history of anaphylaxis or severe allergic reaction.
10. They have taken part in any other contact lens or care solution clinical trial or research, within two weeks prior to starting this study.
11. They currently wear either the clariti 1day or the DAILIES AquaComfort Plus lens.

#### 2.2 Subject discontinuation

In general, subjects should be discontinued at any time, if it is in their best interests, as judged by the investigator. Reasons for this may include clinical signs of grade 3 or more, lack of motivation, discomfort, repeated refusal to follow instructions or the use of non-study products such as solutions or lenses. Subjects will be discontinued if a serious adverse event occurs or if they miss two or more planned consecutive visits. Subjects who fail to satisfy all the inclusion and exclusion criteria will be discontinued and replaced. Subjects may choose to leave the study at their own request. All discontinuations will be carefully recorded.

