#### 1.5.1 Power analysis

Assessment using a dataset from a similar, previous study found that a power of 0.8 or greater is provided by 65 completing subjects for the following measures: subjective comfort at lens dispensing, subjective comfort at the start and end of the day, overall subjective comfort, subjective vision, [REDACTED] and for the following biomicroscopic signs: conjunctival and limbal redness, corneal staining, conjunctival staining and papillary

conjunctivitis. This analysis assumes a two-tailed paired analysis and an alpha of 0.05. To allow for discontinuations, 70 subjects will be recruited.

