## Section 2. Resources

### 2.1 Subject selection

In this work 70 subjects will be recruited and enrolled.

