#### 2.1.1 Subject withdrawal and replacement

This study includes three clinical visits. Once the study consent form is signed, the subject is considered to be enrolled on the study. Subjects who have signed the consent form, but who have not completed the dispensing visit will usually be replaced. All subject data will be included in the final analyses unless there are strong grounds for exclusion; such grounds will be detailed in the final report. At the end the study, all subjects will sign a study exit form.

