#### 3.2.2 Dispensing 1 visit

The subject will have received a study-specific information form outlining the study at least 24 hours before the consent visit, and will then be required to sign an informed consent form prior to enrolment [REDACTED]. A copy of the signed form will be issued to the subject. When the subject has signed the consent form, they are considered to be enrolled on the study.

Subjects will be instructed on the following:

1. Lens handling, application and removal, where necessary.
2. Specific study instructions, such as the importance of not using any other contact lens products.
3. General contact lens information such as the management of red eyes.

The following procedures will be performed (any ocular measurement procedures outlined below will be carried out on each eye):

1. Details of the ocular and medical histories and contact lens-wearing history of the subject will be noted [REDACTED]
2. [REDACTED]
3. [REDACTED]
4. [REDACTED]
5. Slit lamp biomicroscopy will be carried out for the signs outlined in Table 4 and in accordance with the current Eurolens Research Standard Operating Procedure 'Examination of the anterior segment using slit lamp biomicroscopy'. Grades will be scored to the nearest 0.1 unit in the best judgement of the investigator using Efron Grading Scales. Corneal staining will be graded for five regions (central, superior, temporal, inferior and nasal) as well as an 'overall' grade. The predominant type of corneal staining present will also be recorded.

Classification	Primary signs	Secondary signs
Signs	Conjunctival redness Limbal redness [REDACTED] Corneal staining [REDACTED] Conjunctival staining Conjunctival indentation Papillary conjunctivitis	Blepharitis Meibomian gland dysfunction Mucous bands
Score	Efron Grading Scales (scored to nearest 0.1)	Efron Grading Scales (scored to nearest 0.1) (except mucous bands, where the number is recorded).

Table 4: Biomicroscopic signs. Staining assessed with sodium fluorescein.

The presence of any ocular adverse events will be recorded, and reported as appropriate [REDACTED]

6. The investigator will confirm that the subject satisfies all the inclusion and exclusion criteria. Subjects who fail to meet all the criteria at this time will usually be discontinued and replaced. If in the opinion of the investigator, the subject may be eligible at a later date, the subject may be brought back for up to ONE repeat visit of this type.

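### Do the three differently worded replacement rules leave a subject who fails fit or acuity on the second lens without a usable status?

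*Combined protocol and SAP*

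**What the plan says.** Three places in the combined protocol and SAP deal with replacement.

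- Section 2.2 is unqualified and has no time limit: "Subjects who fail to satisfy all the inclusion and exclusion criteria will be discontinued and replaced".
- Section 2.1.1 covers early losses: "Subjects who have signed the consent form, but who have not completed the dispensing visit will usually be replaced".
- Section 3.2.2, step 6, covers the eligibility check at the first dispensing visit: "Subjects who fail to meet all the criteria at this time will usually be discontinued and replaced". As an alternative, if the investigator thinks the subject may qualify later, "the subject may be brought back for up to ONE repeat visit of this type".

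Inclusion criterion 7 in section 2.1.3 reads "They can be satisfactorily fitted with the study lens types", and criterion 8 sets an acuity threshold with the study lenses. Both therefore concern both products.

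On numbers, section 2.1 states "In this work 70 subjects will be recruited and enrolled", and section 2.1.1 counts enrolment from consent: "Once the study consent form is signed, the subject is considered to be enrolled on the study". Section 1.5.1 bases power on 65 completers and adds "To allow for discontinuations, 70 subjects will be recruited".

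**The concern.** The visible eligibility check (step 6) comes before either lens goes on the eye. The first lens is fitted at step 7 and the second at step 13 of Follow-up 1, about a week later. Follow-up 1 then repeats points 8 to 14 of the first dispensing visit, but not step 6. A subject who cannot be fitted with the second lens, or misses the acuity threshold with it, has by then been randomised and has worn the first lens for a week. Section 2.2 would replace that subject. Section 2.1.1 and step 6 do not extend that far.

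One could therefore ask whether this subject is ineligible and replaced, or a post-randomisation loss taken from the allowance of five. The answer affects how many subjects are enrolled and how many complete pairs result. It also affects whether the event is reported as an ineligible subject or as a failure of that lens. In a study comparing the clinical performance of two lenses, that last distinction deserves a look.

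**Working it through.** **Scope of the passages**

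1. Criteria 7 and 8 refer to the study lenses in the plural, so failing either one on the second lens is failing an inclusion criterion.
2. Section 2.2 applies to any such failure, at any time. Read literally, it gives the answer: discontinued and replaced.
3. Section 2.1.1 speaks of subjects who have not finished the dispensing visit. Section 3.1 describes one initial dispensing visit and two follow-up visits, so this means the first visit. It says nothing about later failures and does not forbid replacing them.
4. Step 6 is limited to the time of that check. The optional repeat visit is compatible with section 2.2, because a subject who returns and qualifies has not failed the criteria.
5. The passages therefore differ in reach and in firmness, but no subject is given two incompatible instructions.

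**What cannot be seen**

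Criterion 8 needs an acuity result at dispensing, yet no visible step measures acuity, so that step is probably among the redacted ones. Points 8 to 10 of the first dispensing visit come straight after lens fitting, are redacted, and are among those repeated for the second lens. The entries after the second fitting in Table 1 are redacted as well. Steps 2 to 4 could also hold a trial fitting.

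**Effect on the number of pairs**

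Inputs from section 1.5.1: 65 completers, power 0.8 or greater, two-tailed paired analysis, alpha 0.05, 70 recruited. The allowance is 70 − 65 = 5, or 5/70 = 7.1%.

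The figure of 65 cannot be reproduced, because no effect size or standard deviation is readable. It can be inverted. With power set at exactly 0.80, the normal approximation gives d = (1.960 + 0.842)/√65 = 0.347 standard deviations of the paired difference. The noncentral t gives d = 0.353. Power at that d, with n − 1 degrees of freedom and noncentrality d√n, is:

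| Complete pairs | Power |
|---|---|
| 70 | 0.829 |
| 68 | 0.818 |
| 66 | 0.806 |
| 65 | 0.800 |
| 64 | 0.794 |
| 63 | 0.787 |
| 60 | 0.767 |

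The plan claims 0.8 or greater, so these values are floors.

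The documents give no failure or dropout rate. Assume other losses q of 2% to 5% and second-lens failure f of 1% to 5%.

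- Not replaced, expected pairs are 70(1 − q)(1 − f): from 70 × 0.98 × 0.99 = 67.9 down to 70 × 0.95 × 0.95 = 63.2.
- Replaced, expected pairs are about 70(1 − q): from 68.6 down to 66.5, with roughly 71 to 74 subjects enrolled.

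At the unfavourable end this compares about 66 pairs (0.806) with about 63 (0.787), a difference of about 0.02. At the favourable end the gap is 68.6 − 67.9 = 0.7 of a pair, worth less than 0.01.

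**Effect on the comparison**

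A subject who cannot wear the second lens has no one-week score for it, whichever label is used. The set of complete pairs among those already randomised is the same under both readings. Replacement only adds further pairs.

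**The case for a change.** The strongest case for a change is about reporting. Inability to fit one product is itself evidence on clinical performance. If such a subject is classed only as ineligible and replaced, a failure of that lens could disappear from the results, and the classification is better settled before data are seen. One reconciling sentence would cost almost nothing. The wordings also differ whatever the redacted steps contain, and the chance of reaching 65 completers does depend on the reading. With 5% other losses and 5% second-lens failures (both assumed), it is 0.31 without replacement and 0.86 with it.

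Part of this stands. The three passages are not aligned, and the visible text does not promise a table of fit or acuity failures by lens.

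The rest carries less weight. Section 2.2 requires discontinuations to be recorded. Section 2.1.1 keeps all data unless there are strong grounds for exclusion, which the report must set out. Section 3.4 allows partial datasets and requires the number analysed to be given. The event would therefore not vanish. Missing 65 by one or two costs little, since power is 0.787 at 63. Failure on the second lens alone also looks unlikely: entrants are recent soft-lens wearers with at most 1.00 DC of astigmatism, and Table 2 shows two lenses of similar geometry with the same power range, covering every eligible prescription. Enrolment rising above 70 is simply what replacement means. Going further and restricting the score comparisons to subjects who could wear both lenses would sit badly with the rule in section 2.1.1 that data are kept.

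**Conclusion.** The concern does not call for a change. It identifies a real but editorial difference in wording: one passage is firm and unlimited in time, and two are softer and tied to the first visit. On the visible text section 2.2 already covers a second-lens failure, and nothing elsewhere contradicts it. Analysts following the plan as written would record the discontinuation, keep the subject's data or explain why not, and report the numbers analysed. That gives a sound result under either label.

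The one-week paired scores are not biased by the choice. The effect on power is about 0.02 at the unfavourable end of the assumed range and below 0.01 at the favourable end. This rests on power being taken as 0.80 at 65 completers, which is a floor, and on failure and loss rates that are assumptions because the documents give none. It also rests on the readable text; the redacted steps may settle the matter outright. If the protocol is reissued for another reason, the three passages can be aligned then.

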#### 2.3 Safety parameters, adverse events and concurrent illnesses

The key safety parameters are the serious and significant adverse events [REDACTED] (adverse events are classified as 'serious', 'significant' or 'non-significant'). Clinical assessment is made at the study visit(s) for these parameters. The presence of any *ocular* adverse event will be reported on the case report forms and those described as 'serious' or 'significant' will be detailed in the final report. Similarly, any concurrent illness that is likely

to impact on the relevance and quality of the captured data will be noted on the case report form.

### 2.3.1 Investigator obligations

At all times the investigator will act in the best interest of the subject. Referral or treatment of an adverse event or other clinical finding should be initiated in the best clinical judgement of the investigator, irrespective of the participation in the clinical study.

### 2.3.2 Reporting obligations

In the case of a 'serious' or 'significant' ocular adverse event, the Principal Investigator will notify the Industrial Contact Person as soon as possible. Manchester UREC and any regulatory authorities will be informed as required.

## 2.4 Study termination

If it becomes necessary to terminate the study earlier than planned, the Industrial Contact Person will notify the Principal Investigator who will end the study with the cooperation of other staff members. Manchester UREC will be informed. Device deficiencies will be recorded and reported to the Industrial Contact Person.

## 2.5 Protocol deviations

Any deviations from this protocol will be recorded, and reported to the Industrial Contact Person as appropriate. Manchester UREC will be informed as necessary.

### 2.5.1 Protocol amendments

Any amendments will be agreed between the Industrial Contact Person and the Principal Investigator with the cooperation of other staff members. Amendments will be recorded, identified and distributed. Approval from Manchester UREC will be obtained as necessary.

## 2.6 Study resources

Study products will be stored according to the manufacturers' product instructions.

### 2.6.1 Lenses

Details of the study lens are provided in Table 2. Both lens types are CE marked. Initial lens selection will be as indicated by the manufacturer fitting guidelines.

	Lens A	Lens B
Name	cart 1day	DAILIES AquaComfort Plus
Manufacturer	CooperVision	Acon
Material	Somofcon A	Nefcon A
BOZR (mm)	8.6	8.7
Diameter (mm)	14.1	14.0
Spherical powers (D)	-0.50 to -6.00 (0.25 steps)	-0.50 to -6.00 (0.25 steps)

Table 2: Study lenses.

**2.6.1.1 Use of lenses**

Both lens types will be worn on a daily wear, daily disposable basis (i.e. removed at end of day and discarded). Lenses should be worn for a minimum of eight hours per day, five days per week. The lenses are also to be worn for a minimum of two hours before attending the follow-up visits.

**2.6.2 Care regimen**

No care system will be used on this study.

**2.6.3 Inventory control**

Clarity 1day lenses will be supplied by CooperVision Inc. DAILIES AquaComfort Plus lenses will be sourced by Eurolens Research. All worn lenses will be discarded. Unworn lenses will be returned to:

[REDACTED]

**2.6.4 Clinical equipment**

Clinical equipment is regularly maintained and calibrated as required. Standard operating procedures and international standards are used where appropriate.

**2.7 Study control**

This study is controlled by cross-comparison. Bias will be minimised by randomising the order of assessment. Subjects will be masked to the two lenses - lenses will be over-labelled. Masking may be 'broken' if deemed necessary, by the Principal Investigator or Industrial Contact Person. Masking will be broken at the end of the Follow-up 2 visit – step 3 (Section 3.2.3), to allow the subject to answer a number of agreement questions relating to the lens brands.

**2.8 Documentation**

Documents related to this work that require archiving will be kept by Eurolens Research for a period of 10 years after completion of the final report. The Sponsor's permission will be sought before the documents are destroyed.

## 2.9 Data collection and analysis

Data collected in this work will be recorded on a custom developed database and an established data trail. Data handling will include export of the study information from the clinical database into spreadsheet format for manipulation, followed by export into a statistical package for analysis. Most clinical data will be entered directly onto the electronic case report form and is considered to be source data. Data from paper diaries will be inputted onto an excel spreadsheet, with the paper diaries retained and considered source data.

## 2.10

[REDACTED]

## 2.11 Study completion

The clinical phase of the study will be considered as complete when all subjects have signed the exit statement.

## 2.12 Confidentiality

All matters related to this work will remain confidential within Eurolens Research, the funding company and any regulatory authority (e.g. Manchester UREC). Eurolens Research will take all reasonable steps to ensure that specific lens-related information is not passed on to study participants unless this is required for clinical management of an adverse event. Personal subject information will not be made available. To cater for this, subjects will only be referred by their unique identity number in the study report. The data activities of Eurolens Research are registered with the data protection officer at The University of Manchester.

## 2.13 Study monitoring

In order to provide quality control and quality assurance as part of this work, the study monitor will:

1. Liaise closely with the Principal Investigator.
2. Monitor and ensure the safety of the subjects.
3. Ensure that the investigation is being conducted according to the protocol.
4. Monitor and review (or oversee review of) the study records to ensure accuracy.
5. Document their observations and make them available to relevant authorised parties (e.g. Manchester UREC).
6. Implement the Eurolens Research clinical monitoring standard operating procedure.

**2.14 Clinical trial registration**

This study will be registered with [clinicaltrials.gov](http://clinicaltrials.gov) in accordance with section 801 of the Food and Drug Administration (FDA) Act which mandates the registration of certain clinical trials of drugs and medical devices.

## Section 3. Subject management

### 3.1 Visit scheduling

Subjects will be required to attend three visits – an initial dispensing visit and two follow-up visits, after one week of contact lens wear for each lens type. Acceptable date ranges are shown in Table 3.

Visit	Target	Allowable range
Dispensing 1	N/A	N/A
Follow-up 1/Dispensing 2	7 days from Dispensing 1	6-10 days from Dispensing 1
Follow-up 2	7 days from Dispensing 2	6-10 days from Dispensing 2

Table 3: Visits and allowable ranges.

#### 3.1.1 Unscheduled visits

Subjects who attend at their own volition, (or as instructed to do so by the investigator) rather than for a scheduled study visit, will be examined and the visit will be classified as 'unscheduled'. Data collected at these visits will be recorded on the clinical study database.

#### 3.1.2 Missed visits

Subjects not attending for a visit will be contacted and encouraged to return for assessment. If two consecutive study visits are missed, the subject will be discontinued. It is expected that Eurolens Research personnel will attempt all reasonable means of communication in this event, including corresponding with the subject by letter.

### 3.2 Visit conduct

#### 3.2.1 Pre-enrolment

Prior to the dispensing visit, each subject will be asked to watch a short on-line information presentation detailing study visits and procedures. They will be asked to complete several multiple-choice questions to gauge their understanding of the study. Upon successful completion of these questions, the subject will be booked to attend the Dispensing 1 visit. *Subjects should be asked to attend this visit not having worn their habitual contact lenses on the day of the visit.*

#### 3.2.2 Dispensing 1 visit

The subject will have received a study-specific information form outlining the study at least 24 hours before the consent visit, and will then be required to sign an informed consent form prior to enrolment [REDACTED]. A copy of the signed form will be issued to the subject. When the subject has signed the consent form, they are considered to be enrolled on the study.

Subjects will be instructed on the following:

1. Lens handling, application and removal, where necessary.
2. Specific study instructions, such as the importance of not using any other contact lens products.
3. General contact lens information such as the management of red eyes.

The following procedures will be performed (any ocular measurement procedures outlined below will be carried out on each eye):

1. Details of the ocular and medical histories and contact lens-wearing history of the subject will be noted [REDACTED]
2. [REDACTED]
3. [REDACTED]
4. [REDACTED]
5. Slit lamp biomicroscopy will be carried out for the signs outlined in Table 4 and in accordance with the current Eurolens Research Standard Operating Procedure 'Examination of the anterior segment using slit lamp biomicroscopy'. Grades will be scored to the nearest 0.1 unit in the best judgement of the investigator using Efron Grading Scales. Corneal staining will be graded for five regions (central, superior, temporal, inferior and nasal) as well as an 'overall' grade. The predominant type of corneal staining present will also be recorded.

Classification	Primary signs	Secondary signs
Signs	Conjunctival redness Limbal redness [REDACTED] Corneal staining [REDACTED] Conjunctival staining Conjunctival indentation Papillary conjunctivitis	Blepharitis Meibomian gland dysfunction Mucous bands
Score	Efron Grading Scales (scored to nearest 0.1)	Efron Grading Scales (scored to nearest 0.1) (except mucous bands, where the number is recorded).

Table 4: Biomicroscopic signs. Staining assessed with sodium fluorescein.

The presence of any ocular adverse events will be recorded, and reported as appropriate [REDACTED]

6. The investigator will confirm that the subject satisfies all the inclusion and exclusion criteria. Subjects who fail to meet all the criteria at this time will usually be discontinued and replaced. If in the opinion of the investigator, the subject may be eligible at a later date, the subject may be brought back for up to ONE repeat visit of this type.
7. The first randomised lens pair will be fitted and allowed to settle for five minutes. The subject will be masked to the lens brand.

8. [REDACTED]

9. [REDACTED]

10. [REDACTED]
11. The subject will be asked to score the following subjective scores with reference to appropriate vertical visual analogue scales (0-100) [REDACTED]
  - Comfort
  - Vision
  - Overall score

12. [REDACTED]

Subjects will [REDACTED] be given a supply of contact lenses which will be over-labelled to maintain masking, for the first study period.

13. [REDACTED]  
[REDACTED]  
[REDACTED]  
[REDACTED]

14. The subject will then be discharged and asked to return for the one-week follow-up visit wearing the study lenses for at least two hours. Subjects should be asked to wear their lenses for a minimum of eight hours per day, five days per week.

